**Tailoring Surgical Management of Multifocal
Breast Cancer:is There a Possibility**

NCT03900299

Document Date: December 2, 2019

Data Management and Analysis:

The collected data was revised, coded, tabulated and introduced to a PC using Statistical package for Social Science (**IBM Corp. Released 2011. IBM SPSS Statistics for Windows, Version 20.0. Armonk, NY: IBM Corp.**). Data was presented and suitable analysis was done according to the type of data obtained for each parameter as follow :.

I-Descriptive statistics:-Frequency and percentage of qualitative variables.

II-Analytical statistics:

1. Chi-Square test was used to examine the relationship between two qualitative variables

2. Fisher's exact test: was used to examine the relationship between two qualitative variables for 2x2 tables (tables with 4 cells), when the expected count is less than 5 in more than 20% of cells

3-Monte Carlo-test was used to examine the relationship between two qualitative variables for larger than 2x2 tables (tables with more than 4 cells) when the expected count is less than 5 in more than 20% of cells

- P- value: level of significance

-P>0.05: Non significant (NS).

-P< 0.05: Significant (S).

-P<0.01: Highly significant (HS).

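### The SAP's switch to the Monte Carlo test sets no minimum for a single cell, so some tables larger than 2x2 with a nearly empty cell can stay on Chi-square and receive a false HS label

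*SAP*

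**What the plan says.** Under Analytical statistics, item 1 of the SAP is general: "Chi-Square test was used to examine the relationship between two qualitative variables". Items 2 and 3 replace Chi-square when expected counts are small. Fisher's exact test is used "for 2x2 tables (tables with 4 cells), when the expected count is less than 5 in more than 20% of cells". The Monte Carlo test is used for "tables with more than 4 cells) when the expected count is less than 5 in more than 20% of cells". Neither the SAP nor the protocol adds a lower limit for an individual cell.

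Results are then labelled at two levels: "P< 0.05: Significant (S)" and "P<0.01: Highly significant (HS)".

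**The concern.** The same 20% share is applied to every table size, but it protects only the 2x2 table, where one small cell is already 25% of the cells. In a larger table one cell can be a smaller share than 20%. Its expected count can then be well below 1 without triggering the switch.

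The Chi-square approximation is poor in that situation. One or two extra patients in the nearly empty cell can supply almost the whole statistic, and the reference distribution understates how often that happens by chance, mainly far out in the tail. At stake is the correctness of the S and HS labels, chiefly HS, in Group A tables that cross focality with a tumor feature recorded in three or more categories. Tumor grade would be one example if it is tabulated that way.

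**Working it through.** **Inputs.** From the SAP: the switch rule and the thresholds 0.05 and 0.01. From the protocol's Introduction: a published incidence of multifocal and multicentric disease of 6% to 60%. The documents give no table counts and no sample size, so there is no planned figure to reproduce. All margins below are assumptions.

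**Step 1: cells that may fall below 5 without a switch.**

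| Table | Cells | Largest number not above 20% | Share |
|---|---|---|---|
| 2x2 | 4 | 0 | one cell would be 25% |
| 2x3 | 6 | 1 | 16.7% |
| 2x4 | 8 | 1 | 12.5% |
| 3x3 | 9 | 1 | 11.1% |
| 2x5 | 10 | 2 | exactly 20%, which is not more than 20% |

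**Step 2: when a 2x3 or 2x4 table falls in the gap.** Let p be the multifocal share and n the number of patients in the rare category. The small cell has expected count np and the other cell in that column n(1-p). The table stays on Chi-square with a cell below 1 only if np < 1 and n(1-p) >= 5, with all other cells at least 5. Together these give p/(1-p) < 1/5, so p < 1/6.

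- p = 6%: n from 6 to 16
- p = 10%: n from 6 to 9
- p = 15%: n = 6 only
- p = 17%: no n qualifies

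**Step 3: exact size in gap tables.** With both margins fixed, every possible 2x3 table was enumerated with its hypergeometric probability. The true error is the total probability of tables whose Chi-square P value (2 degrees of freedom) is below the threshold.

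| Rows; columns | Smallest expected count | True error at 0.05 | True error at 0.01 |
|---|---|---|---|
| 50/450; 6/247/247 | 50 x 6/500 = 0.60 | 4.3% | 2.0% |
| 15/185; 6/97/97 | 15 x 6/200 = 0.45 | 8.7% | 1.5% |
| 16/447; 9/161/293 | 16 x 9/463 = 0.31 | 5.1% | 3.7% |
| 60/940; 10/495/495 | 60 x 10/1000 = 0.60 | 4.9% | 2.4% |
| 20/180; 8/96/96 | 20 x 8/200 = 0.80 | 5.7% | 1.3% |

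Each of these has exactly one cell in six below 5. A comparison table with every expected count at least 5 gave 5.1% and 1.1%.

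**Step 4: how a label changes.** The exact P value is the quantity that the Monte Carlo test estimates.

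- Rows 50/450, multifocal counts 3, 23, 24: the small cell alone contributes (3 - 0.6)²/0.6 = 9.60 of a total statistic of 10.82. Chi-square P = 0.0045 (HS); exact P = 0.017 (S only).
- Rows 16/447, counts 2, 5, 9: Chi-square P = 0.0079 (HS); exact P = 0.037 (S only).
- Rows 15/185, counts 2, 7, 6: Chi-square P = 0.049 (S); exact P = 0.087 (NS).

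**Step 5: typical size.** In 300 randomly drawn 2x3 gap tables (N 60 to 499, rarest column 1 to 14 patients):

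- At 0.01 the median true error was 1.4% (range 0.8% to 3.7%); 98% of tables exceeded 1% and 19% exceeded 2%.
- At 0.05 the median was 5.1% (range 3.4% to 8.2%); 20% exceeded 6%.

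**Step 6: how often the gap applies.** Among randomly drawn 2x3 tables from the same assumed ranges with a cell below 1, 7,964 of 73,853 (10.8%) stayed on Chi-square. The rest already switched.

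**The case against.** The strongest reply is that the gap is narrow and its consequence small. Much of this stands.

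- **Reach.** A reader might infer that any table with a nearly empty cell stays on Chi-square. The rule does not do that: about nine in ten such tables in the assumed sweep switch, and in a 2x3 or 2x4 table the gap closes once the multifocal share reaches one sixth. Most of the 6% to 60% range in the protocol's Introduction lies above that.
- **Objectives.** A reader might also infer that the comparison of multifocality with use of mastectomy (secondary objective 2) is exposed. The protocol's Methods list two types of operation and two focality classes, which is a 2x2 table, where the rule works. The age split at 35 years is likewise binary. Recurrence in Group A is to be analysed by Kaplan-Meier, log-rank and Cox methods, which this rule does not touch.
- **The S label.** A general claim that S labels are too frequent is not supported. The median error at 0.05 is 5.1%, the same as in the comparison table with no small cell, and some gap tables are conservative.
- **Overall error.** When the whole SAP rule was simulated with random margins (N = 500, 10% multifocal), the error at 0.01 was 1.4% with a rare category of 1.4% and 1.2% with one of 5%. At 0.05 it was 4.9% and 4.7%.
- **Consequence.** Nothing in the documents makes a decision depend on HS.

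What does not stand is that the rule is therefore adequate. It attaches a label at P<0.01, where nearly every gap table in the sweep exceeded its nominal error, and the SAP already contains the test that would prevent this.

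**Conclusion.** The concern holds as a minor wording gap in SAP item 3. Inside the gap the true error at P<0.01 is typically about 1.4% and up to about 3.7%, so some HS labels would be false. At P<0.05 it averages about 5%, with isolated tables at 8% to 9%.

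These figures rest on assumed 2x3 margins. The documents fix neither the categories of any variable with three or more levels nor any count, so it cannot be said that a real table of this study is affected. It would also go too far to conclude that every table with an expected count below 5 needs the Monte Carlo test. The calculations concern tables with a cell below 1 and do not show a material problem elsewhere.

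**What to change.** Reword item 3 so that, for tables larger than 2x2, the Monte Carlo test is used when more than 20% of cells have an expected count below 5 **or any expected count is below 1**. Limit item 1 to the tables that neither item 2 nor item 3 covers. Item 2 needs no change.

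The cost is one clause in the SAP. The test is already planned, no further data are needed and computing time is negligible. A few P values will become slightly less favourable. If tables have already been produced, only those larger than 2x2 with an expected count below 1 that were tested by Chi-square need to be re-run.
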